#### **3.3.1.3.2 Partial end dates**

If the year is unknown, then the date will not be imputed and will be assigned a missing value.

If the month is unknown, then assign July.

If the day is unknown, then assign the day as mid-month (14th for February, 15th for all other months).

If the above rules for end dates result in illogical date (i.e. end date < start date or end date > participant's date of completion/discontinuation) with regards to the dates the participant was in the study, then the end date will be replaced with the participant's date of completion/discontinuation.

### **3.3.1.4 Handling of Missing Data**

#### **3.3.1.4.1 Handling of Missing Efficacy Data**

Participants with missing data for the primary efficacy endpoint of occurrence (yes/no) of normokalaemia (NK) ( $K^+$  between 3.5 and 5.0 mmol/L, inclusive) at 180 days post-discharge will be treated as non-responders for the main analysis. Additionally, participants who receive rescue medication for HK during the outpatient period will also be deemed as non-responders, regardless of any subsequent measurement for  $K^+$ .

$K^+$  measurements up to 180 days post-discharge will be analysed using mixed-effects models repeated measures, which assumes that missing outcomes are missing at random (MAR). Details of this analysis are provided in section 4.2.13.

#### **3.3.1.4.2 Handling of Missing Safety Data**

In general, missing clinical laboratory data, vital signs and ECG data will not be imputed. Adverse event imputations for missing intensity or relationship are given in section 4.6.2.1. Unknown or partial medication and AE date imputations are given in section 3.3.1.3 and are to be used only for the assessment of prior / concomitant status for medications and treatment-emergent status for AEs.

### **3.3.2 Visit Window**

For all populations, assessments will be assigned to visits and analysis periods for categorical summaries as follows:

- Assessments with missing data and assessments marked “Not Done” will be considered as providing a missing response and are not permitted to be assigned to a visit window.
- The worst value (e.g. out of reference range preferred to within range; abnormal preferred to normal) will be used in each window. If multiple assessments fall within the same window with equal value, then the first non-missing value will be used for the summary.
- In the AZ Standard TFL shells, “Time Point” is used interchangeably with “Visit” as, in this study; multiple observations are not made at the same visit.

Target day and protocol/analysis visit windows in Table 2 and Table 3 are with respect to the date of randomisation. Visit windowing related to the date of hospital admissions and ED visits will use Table 2. All other assessments will use visit windowing provided by Table 3. Alternative windowing is required because outpatient phase visits 5, 6, 8 and 9 are conducted by phone and collect information on concomitant medication, adverse events, hospital admission and ED visits only. Target day and protocol analysis visit windows in Table 4 are with respect to the date of last dose of SZC (EOT).

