- ^k Treatment with sodium zirconium cyclosilicate (SZC) will be established while the participant is in the hospital. Only participants randomised to SZC will be dispensed study intervention during the outpatient phase. Any time study drug dose is adjusted, or if in either treatment arm a concomitant medication which may affect K⁺ levels is changed (eg, use of renin angiotensin-aldosterone system inhibitors [angiotensin-converting enzyme inhibitors, angiotensin receptor blocker, mineralocorticoid receptor antagonists] or diuretics), the participant needs to return to the site 7 (± 2) days later for a K⁺ measurement and recording of adverse events and concomitant medications. During the inpatient phase, drug dispensation will occur every day.
- ^l Central laboratory K⁺ results at baseline are not necessary to initiate the study intervention as long as all eligibility criteria are met (only local assessment of K⁺ within 24 hours of treatment initiation is required).
- ^m If dose titration occurs at any time during the outpatient phase, unscheduled dispensation visits will be performed.
- ⁿ Relative to the date of randomisation (Visit 3)
- ^o Relative to the date of Visit 10/EOT.

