^a Any time study drug dose is adjusted, or if in either treatment arm, a concomitant medication which may affect K⁺ levels is changed (eg, use of RAASi or diuretics), the participant needs to return to the site 7 (\pm 2) days later for a K⁺ measurement and recording of adverse events and concomitant medications.

Participants randomised to Arm B will be discharged without SZC and will receive SoC per local practice for managing their K⁺ until the EOT (180 days post-discharge). The SoC will be at the discretion of the treating physician; however, participants intended to be discharged with a K-binder will not be randomised. However, participants in Arm B may have a K-binder prescribed at Day 7 post-discharge (or after Day 7 post-discharge) to treat confirmed HK or in case there is an increase in K⁺ level since discharge that, in the investigator's opinion, requires therapy.

The K⁺ levels will be measured at on-site visits at Days 7 (local laboratory), 90 (local and central laboratories), and 180 (local and central laboratories) (see Sections 8.1.1 and 8.2.4). Overall monitoring frequency will depend upon a variety of factors including other medications, progression of CKD, and dietary K⁺ intake. It is the responsibility of the treating physicians to check the participant K⁺ as medically appropriate/in accordance with the label (for both SZC and SoC arms). In addition to the scheduled on-site visits, participants should return to the site for a local K⁺ measurement 7 (\pm 2) days after any dose adjustment to SZC.

Additionally, participants in either treatment arm should have their K⁺ measured locally 7 (\pm 2) days after changes are made to medications that affect K⁺ levels (eg, use of RAASI or diuretics).

Such additional K⁺ checks and site visits will take place as clinically indicated and the resulting data, including AEs and concomitant medication information, relating to these visits will also be collected during the study.

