7 DISCONTINUATION OF STUDY INTERVENTION AND PARTICIPANT DISCONTINUATION/WITHDRAWAL

7.1 Discontinuation of Study Intervention

7.1.1 Permanent Discontinuation of Study Intervention

It may be necessary for a participant to permanently discontinue (definitive discontinuation) study intervention. If study intervention is permanently discontinued, the participant will be followed up according to the SoA ([Table 1](#)). See the SoA for data to be collected at the time of discontinuation of study intervention and follow-up for any further evaluations that need to be completed.

To minimize risk for events related to severe hypokalaemia, the following discontinuation criterion will be followed:

- Confirmed $K^+ < 3.0$ mmol/L by taking a second measurement after a ≥ 10 -minute interval, at any time during the study, the participant should immediately receive appropriate medical intervention and study intervention should be permanently discontinued.

To minimize risk for events related to severe HK, the following discontinuation criterion will be followed:

- Confirmed $K^+ > 6.0$ mmol/L by taking a second measurement after a ≥ 10 -minute interval, at any time during the study, the participant should immediately receive appropriate medical intervention and study intervention should be permanently discontinued.

To minimize risk for events related to prolongation of QT interval corrected (QTc), the following discontinuation criteria will be followed:

- If an absolute QTc > 550 ms, or an increase in QTc interval > 60 ms from baseline to more than 500 ms is reached, the participant should immediately receive appropriate medical intervention and be permanently discontinued from the study intervention. The QTcF algorithm is recommended. All participants meeting the QTc > 500 ms criterion should immediately have K^+ assessed, if not already done within 1 hour of performing the electrocardiogram (ECG).

For serious arrhythmia (eg, associated with $K^+ < 3.5$ or > 5.6 mmol/L), study drug should be permanently discontinued.

Other reasons for discontinuation of study intervention may include:

- Participant decision; the participant is at any time free to discontinue treatment, without prejudice to further treatment.
- Incorrectly randomised participant, in whom the inclusion/exclusion criteria violation would put the participant at undue risk. This will require a discussion with the medical team, who will provide a final outcome / action.

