### **3.3.1 General Study Level Definitions**

During the in-hospital phase, all assessment days will be related to the first day of first dose of study intervention SZC. Day 1 of the in-hospital phase is defined as first dose of study intervention SZC. During the outpatient phase, all assessment days will be related to the date of randomisation. Day 1 of the outpatient phase is defined as the date of randomisation. During the follow-up phase, all assessment days will be related to the last dose of SZC. Day 1 of the follow-up phase is defined as the last dose of SZC + 1.

The date of the first dose of SZC for each subject will be taken from the Drug Accountability (Inpatient) eCRF page. If the date in this eCRF page is missing, alternatively the date of first dose dispensed will be used.

The date and time of randomisation will be as recorded in the IRT system. Relative days after day 1 are calculated as (assessment date – day 1 date) + 1. Relative days prior to day 1 are calculated as (assessment date – day 1 date). The day prior to day 1 is day -1. Day 0 is not defined.

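### The SAP times the follow-up visit (Visit 11) from the last SZC dose, so no protocol-compliant Visit 11 in Arm B normally falls in its own analysis window

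*SAP*

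**What the plan says.** **SAP.** Section 3.3.1 sets the day count for the follow-up phase: "During the follow-up phase, all assessment days will be related to the last dose of SZC", and "Day 1 of the follow-up phase is defined as the last dose of SZC + 1". Section 3.3.2 repeats the anchor for Table 4: "Target day and protocol analysis visit windows in Table 4 are with respect to the date of last dose of SZC (EOT". Table 4 gives Visit 11 a target of EOT+7, a protocol window of EOT+4 to EOT+10 and an analysis window of EOT+1 to EOT+10. Neither section has a separate rule for Arm B. Table 3, which is counted from randomisation, gives Visit 4 Days 2 to 45 and Visit 10 Days 136 to 186, and ends there. Within a window, 3.3.2 takes the worst value.

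**Protocol.** Section 4.1 labels the 180-day visit EOT, without distinction of arm, and puts the follow-up visit about 7 days later. The Schedule of Activities allows ±6 days for Visit 10 and ±3 for Visit 11, and its last footnote reads "Relative to the date of Visit 10/EOT". On treatment, Section 6.2 says "Participants randomised to Arm B will be discharged without SZC and will receive SoC per local practice", and the Schedule adds: "Only participants randomised to SZC will be dispensed study intervention during the outpatient phase". On early stopping, Section 7.1.1 says "If study intervention is permanently discontinued, the participant will be followed up according to the SoA".

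**The concern.** The two anchors roughly coincide only for an Arm A participant who takes SZC up to Visit 10. In Arm B they are about six months apart. In Arm A they separate whenever SZC is stopped early and the participant stays on schedule.

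Visit 11 collects vital signs, weight, ECG and local K+. Protocol 2.3.1 gives it a safety purpose: checking K+ one week after EOT. SAP 4.6.6.2 and 4.6.7.2 summarise vital signs and ECG in the randomised safety set, by treatment received, over all visits at which they are assessed. If the stated rule is programmed as written, the follow-up row of those tables will not hold Arm B's follow-up visit, and some Visit 10 results may be replaced by values taken at Visit 11.

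**Working it through.** **Inputs.** Visit 10 at 180 ± 6 days and Visit 11 at Visit 10 + 7 ± 3 (Protocol 1.3); Visit 4 at 7 ± 1 (Protocol 1.3); analysis windows from SAP Tables 3 and 4. Assumption: Arm B's last SZC dose is 0, 1 or 2 days before randomisation. Days are elapsed days from randomisation. The SAP's own convention, randomisation = Day 1, adds one; its results are in brackets.

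**1. The plan's own figure.** 7 − 3 = 4 and 7 + 3 = 10, which reproduces Table 4's protocol window of EOT+4 to EOT+10.

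**2. Arm B Visit 11 at target.** 180 + 7 = Day 187 [188]. Measured from the last dose this is EOT+187 to EOT+189, outside EOT+1 to EOT+10. It is also past Day 186, the end of Table 3, so it has no window.

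**3. All compliant Arm B schedules.** Let Visit 10 deviate by *a* (−6 to +6) and Visit 11 by *b* (−3 to +3): 13 × 7 = 91 combinations, with Visit 11 on Day 187 + *a* + *b*.
- Earliest: 187 − 9 = Day 178, at least EOT+178. So 0 of 91 reach the Visit 11 window.
- Day 186 or earlier needs *a* + *b* ≤ −1. Seven combinations have *a* + *b* = 0, so by symmetry (91 − 7)/2 = 42 qualify and fall in the Visit 10 window. [*a* + *b* ≤ −2 is needed; 42 − 7 = 35.]
- The rest, 91 − 42 = 49 [91 − 35 = 56], fall in no window.

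These count combinations of dates. They are not probabilities.

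**4. Arm B Day 7 visit.** Days 6 to 8 are EOT+6 to EOT+8 if the last dose is on the day of randomisation, and EOT+8 to EOT+10 if it is two days earlier. Every case tested meets EOT+1 to EOT+10 and also lies in the Visit 4 window. No tie-break is given.

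**5. Arm A early stopper (illustration).** With a last dose on Day 60, the Visit 11 window is Days 61 to 70. The real Visit 11, about Day 187, is EOT+127.

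**6. Arm A completer.** With a last dose on Day 180, the Visit 11 window is Days 181 to 190. Days 181 to 186 also belong to Visit 10.

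**7. After re-anchoring to the Visit 10 date.** Visit 11 is at +4 to +10, so 91 of 91 fall in EOT+1 to EOT+10. The Day 7 visit is at EOT−174 to EOT−172, clear of the window. In 42 [35] combinations Visit 11 still lies on or before Day 186, so a precedence rule is needed as well.

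**The case against.** The strongest reply is that EOT is only loosely glossed. Table 4 itself says EOT+7, and SAP 4.6.7.1 lists EOT as an ECG timepoint alongside the visits, where it means Visit 10. On that reading Table 4 works for Arm B. This shows what was probably intended, but 3.3.1 and 3.3.2 both name the last SZC dose, and a programmer following them would use that date.

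A second reply is that 3.3.2 introduces its windows for categorical summaries, while ECG and vital signs are summarised as continuous data at scheduled timepoints. This does not dispose of the point. Section 3.3.3 sends unscheduled visits in by-visit presentations to 3.3.2, the ECG and vital-sign sections use it to choose among multiple results, and 4.2.2.5 has to switch windowing off explicitly for one K+ analysis.

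Other replies stand, and they limit what may be inferred:
- A reader might infer that Arm B's Day 7 data are moved into the follow-up row, setting Arm A after six months of SZC against Arm B one week after discharge. Table 4 is titled for the follow-up period, and the Day 7 visit stays in the Visit 4 window. At most it is assigned twice.
- A reader might infer that Arm B's Visit 11 never has a window. Early but compliant visits fall in the Visit 10 window.
- A reader might infer that Arm B's follow-up data are lost. ECG and vital-sign data are also listed.
- A reader might infer that early stoppers have no scheduled off-drug assessment. The Schedule has an early-discontinuation visit with vital signs, ECG and K+; it is not Visit 11.
- The Day 181 to 186 overlap in Arm A would exist under the protocol's anchor too. It is a matter of precedence, separate from the anchor.

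**Conclusion.** The SAP's reference date for Visit 11 contradicts the protocol's and should be corrected. As written, it places no compliant Arm B Visit 11 in the Visit 11 window. This concerns about 65 participants (half of 130), except any given SZC later as a binder, which the footnote to Protocol 6.7.1 permits; the SAP does not say whether such doses count. Arm A participants who stop SZC early but stay on schedule have the same misplacement.

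The conclusion assumes that 3.3.1 and 3.3.2 are applied literally and that Arm B's last SZC dose is at or shortly before discharge.

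The effect stops at descriptive by-visit safety summaries of Visit 11 data: ECG, vital signs, weight, and local K+ where tabulated. A reader might infer that the primary endpoint is contaminated when an early Visit 11 falls in the Visit 10 window. The documents do not support that: Protocol 8.1.1 uses central-laboratory K+ for endpoints, and the Schedule has only local K+ at Visit 11. No primary or secondary efficacy test uses Table 4.

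**What to change.** 1. In SAP 3.3.1, 3.3.2 and Table 4, replace the last SZC dose as reference with the date of Visit 10/EOT in both arms. Where Visit 10 was missed, use randomisation date + 180 days.
2. State that, in the by-visit safety summaries, an assessment after the actual Visit 10 date and within Visit 10+1 to Visit 10+10 is assigned to Visit 11 and not to Visit 10. Leave the Table 3 window for the primary-endpoint K+ unchanged, so that the endpoint keeps a single Visit 10 definition.
3. Label the early-discontinuation assessments of participants who stop SZC separately, for example with an off-SZC flag, and not as Visit 11.

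The cost is a few lines of SAP text, one changed reference date and one flag in programming. The downside is that for early stoppers Visit 11 no longer means about one week off SZC; the flag makes this visible.

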**Table 1 Definition of visit windows during the inpatient period**

Visit	Target Day of Visit	Visit Window
Visit 1	Date of Informed Consent	NA a
Visit 2	Date of first dose of SZC	NA

a For potassium measurements only, the visit windowing will allow any potassium measurement recorded prior to the date of informed consent

**Table 2: Definition of visit windows during the outpatient period for hospital admissions and ED visits**

Visit	Study Day a	Target Day of Visit b	Protocol Visit Window b	Analysis Visit Window b
Visit 3	2 to 21	Date of randomisation	NA	NA
Visit 4	9 to 28	7	6 to 8	2 to 19
Visit 5	32 to 51	30	24 to 36	20 to 45
Visit 6	62 to 81	60	54 to 66	46 to 75
Visit 7	92 to 111	90	84 to 96	76 to 105
Visit 8	122 to 141	120	114 to 126	106 to 135
Visit 9	152 to 171	150	144 to 156	136 to 165
Visit 10	182 to 201	180	174 to 186	166 to 186

a Relative to the date of first study intervention dispensation of SZC during the inpatient phase

b Relative to the date of randomisation

**Table 3: Definition of visit windows during the outpatient period for all other assessments**

Visit	Study Day a	Target Day of Visit b	Protocol Visit Window b	Analysis Visit Window b
Visit 3	2 to 21	Date of randomisation	NA	NA
Visit 4	9 to 28	7	6 to 8	2 to 45
Visit 7	92 to 111	90	84 to 96	46 to 135
Visit 10	182 to 201	180	174 to 186	136 to 186

a Relative to the date of first study intervention dispensation of SZC during the inpatient phase

b Relative to the date of randomisation

**Table 4: Definition of visit windows during the follow-up period**

Visit	Target Day of Visit	Protocol Visit Window	Analysis Visit Window
Visit 11	EOT+7	EOT+4 to EOT+10	EOT+1 to EOT+10

### 3.3.3 Handling of Unscheduled Visits

Unscheduled visits will be considered for by-visit presentations and listings according to the rules outlined in Section 3.3.2. All unscheduled visits will be included in listings.

### 3.3.4 Multiplicity/Multiple Comparisons

To control for type I error, a hierarchical testing procedure will be followed when formally testing the primary and secondary efficacy analysis endpoints. The hierarchical testing procedure will follow a stepwise algorithm where each endpoint is only formally tested if the preceding null hypothesis is rejected (two-sided p-value < 0.05). If the preceding null hypothesis is not rejected, then the evaluation of the endpoint will be reduced to that of an exploratory endpoint. The testing order for the primary and secondary efficacy analysis endpoints is displayed in Table 5:

**Table 5: Testing order for primary and secondary efficacy endpoints**

Order	Efficacy Endpoint	Section
1	Occurrence (yes/no) of normokalaemia (NK) ( $K^+$ between 3.5 and 5.0 mmol/L, inclusive) at 180 days post-discharge	4.2.2
2	Time to first occurrence of all-cause hospital admission or ED visit with HK as a contributing factor, or all-cause death, or use of rescue therapy for HK at any time post-discharge up to 180 days inclusive.	4.2.3
3	Time to first occurrence of all-cause hospital admission or ED visit with HK as a contributing factor at any time post-discharge up to 180 days inclusive.	4.2.4
4	Number of all-cause hospital admission or ED visits with HK as a contributing factor, at any time post-discharge up to 180 days.	4.2.5
5	Time to first occurrence of RAASI down-titration (or discontinuation) at any time post-discharge up to 180 days.	4.2.6
6	Time to first occurrence of hospital admission or ED visit, both with HK as a contributing factor at any time post-discharge up to 180 days.	4.2.7
7	Number of hospital admission or ED visits, both with HK as a contributing factor, at any time post-discharge up to 180 days.	4.2.8

### **3.3.5 Handling of Protocol Deviations in Study Analysis**

Protocol deviations are defined as any change, divergence, or departure from the study design of procedures defined in the clinical study protocol (CSP).

Important protocol deviations will be defined by AZ before database lock following the process described in the protocol deviation management plan and the project specific protocol deviations list. Important protocol deviations are a subset of protocol deviations, which may significantly impact the correctness, accuracy, and / or reliability of the study data or that may significantly affect a subject's rights, safety or well-being. The following criteria may be considered as important protocol deviations which may have a major effect on efficacy or that could potentially affect the interpretability of the study results.

1. Informed Consent, such as Informed Consent Form (ICF) not signed before project specific assessments or procedures.
2. Study Conduct/Procedures, such as failure to complete or comply with inclusion/exclusion criteria, including discrepancy within source documentation and / or raw data, non-compliance with protocol / CIP requirements (Note: this does not include ICF issues), use of prohibited medication or prohibited treatment therapy or a subject's first dose date prior to baseline evaluations.
3. Investigational Product, such as inadequate supply of materials/IMP (includes issues with regard to expiration date e.g. subject takes IMP which has expired).
4. Safety, such as non-recording of AEs and SAEs by PIs (e.g. recording on time, etc.).

In addition, protocol deviations will be defined by AZ before database lock as coronavirus disease (COVID)-19 pandemic related or not by judging the root cause of the protocol deviation, in line with US Food and Drug Administration (FDA) guidance (FDA Guidance on Conduct of Clinical Trials of Medical Products during COVID-19 Public Health Emergency; March 2020). These will be identified as protocol deviations, which start with the prefix “COVID19”. The following criteria may be considered indicative of a protocol deviation related to the COVID-19 pandemic.

- Missed in-person visit due to COVID-19 illness and/or COVID-19 public health control measures
- Study visit out of window due to COVID-19 illness and/or COVID-19 public health control measures
- Missed doses due to COVID-19 illness and/or COVID-19 public health control measures

- Missed central laboratory K+ measurements due to COVID-19 illness and/or COVID-19 public health control measures

